8.1.2. The per-protocol (PP) population

The primary and secondary semen analyses will also be conducted on the PP population, defined as all participants who were enrolled and started treatment, excluding:

1. Participants not meeting the definition of having received an adequate amount of treatment.

2. Participants classified as major protocol deviations for analysis (see §7.4).

8.2. TB efficacy analysis populations

The TB efficacy outcomes will be reported by ITT (§8.1.1) and the following populations:

8.2.1. The TB-specific modified intent-to-treat (TB-MITT) population

Defined as all participants who were enrolled and started treatment, excluding those listed below:

- 1. Any late exclusions
 - a. Participants enrolled and later found to be ineligible because of a protocol violation at enrolment (based on data collected prior to enrolment).
 - b. Participants without culture confirmation of TB at Day 1 (baseline) (or screening to week 4 if baseline is contaminated or negative)
- 2. Any participants who completed treatment and were later lost to follow-up or withdrawn from the study.
- 3. Participants who died during treatment from violent or accidental cause.
- 4. Participants who died during follow-up with no evidence of failure or relapse of TB.
- 5. Participants who are able to produce sputum at the endpoint visit, but whose endpoint visit sputum samples are all contaminated or missing, who cannot be brought back for repeat cultures, provided their last positive culture was followed by at least two negative cultures. N.B.: This does not apply to participants who are unable to produce sputum at the given endpoint, or to participants who are able to be brought back subsequently and produce negative cultures.

Participants already classified as having an unfavourable outcome will not be excluded.

8.2.2. The TB-specific per-protocol (TB-PP) population

In addition to those excluded from the TB-MITT population (§8.2.1), the following participants will be excluded:

- 1. Participants lost-to follow-up or withdrawn for reasons other than treatment failure before the end of treatment.
- 2. Participants whose treatment was modified or extended beyond what was permitted.
- 3. Participants not meeting the definition of having received an adequate amount of treatment.
- 4. Participants who classified as major protocol deviations for analysis (see §7.4).

Participants already classified as having an unfavourable outcome will not be excluded.

8.3. The Safety analysis population

The safety and tolerability outcomes will be conducted on the safety population, which in this trial is the same as the ITT population; defined as all participants enrolled who received at least 1 dose of trial treatment.

8.4. Pharmacokinetics (PK) analysis population

Defined as all participants who were enrolled and started treatment, excluding participants who do not have at least one valid PK measurement.

9. Statistical Analysis

All statistical analysis will be based on descriptive statistics for the whole population and by key subgroups.

All statistical analyses tables, listings and figures will be produced using STATA Version 17.0 or higher.

9.1. Primary semen outcome analysis

The change from baseline in total sperm count at 26 weeks will be summarised by mean, standard deviation, median, IQR and range. Both the baseline value and change from baseline will be summarised.

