### Objective of the trial:

This study is intended to rule out clinically significant severe adverse effects on testicular function.

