# 3 Trial Objectives

# 3.1 Primary Objective:

To assess the male reproductive safety of pretomanid in the regimen (BPaMZ) of bedaquiline 200mg daily for 8 weeks then 100 mg daily for 18 weeks, together with pretomanid 200 mg (1x daily) + moxifloxacin 400 mg (1x daily) + pyrazinamide 1500 mg (1x daily) for 26 weeks in participants with Drug-resistant (DR) pulmonary TB.

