### Medical History and Concurrent Conditions:

- 1. Resistant to fluoroquinolones by rapid molecular test.
- 2. History of male infertility or vasectomy.
- 3. Unable to produce semen sample.
- 4. Evidence at screening of azoospermia.
- 5. Known erectile dysfunction that would prevent ejaculation.
- 6. Historical or active disease process of the male reproductive tract that would compromise sperm production. e.g., Tuberculous epididymitis.
- 7. History of any illness that, in the opinion of the Investigator, might confound the results of the study or poses an additional risk to the participant by their participation in the study.
- 8. Abuse of alcohol or illegal drugs that in the opinion of the Investigator would compromise the participants' safety or ability to follow through with all protocol-specified restrictions, visits, and evaluations.
- 9. Being, or about to be, treated for malaria.
- 10. Is critically ill and, in the judgment of the Investigator, has a diagnosis likely to result in death during the trial or the follow-up period.
- 11. TB meningitis or other forms of extrapulmonary tuberculosis with high risk of a poor outcome, or likely to require a longer course of therapy (such as TB of the bone or joint), as judged by the Investigator.

- 12. History of allergy or hypersensitivity to any of the trial IMP or related substances, including known allergy to any fluoroquinolone antibiotic, history of tendinopathy associated with quinolones.
- 13. For HIV infected participants any of the following:
  - a) CD4+ count <100 cells/µL
  - b) Received intravenous antifungal medication within the last 90 days
- 14. Participants with newly diagnosed tuberculosis and HIV that require initiation of appropriate HIV therapy before participants has received at least 2 weeks of an antituberculosis regimen.
- 15. Participants with any of the following at the Screening visit (per measurements and reading done by ECG):
  - a. QTcF interval on ECG >500 msec. Participants with QTcF > 450 must be discussed with the Sponsor Medical Monitor before enrollment.
  - b. Heart failure
  - c. A personal or family history of congenital QT prolongation
  - d. A history of or known, untreated, ongoing hypothyroidism, except for well treated hypothyroidism.
  - e. A history of or ongoing bradyarrhythmia
  - f. A history of Torsade de Pointe
- 16. Unstable Diabetes Mellitus which required hospitalization for hyper- or hypo-glycaemia within the past year prior to start of screening.

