## 9.4 Safety Monitoring

#### **Medical Monitoring:**

During the conduct of the study, it is the responsibility of the sponsor-appointed medical monitor of the study to consult with the investigator(s) and fertility experts regarding any medical concerns or questions that arise. When requested by an investigator, the Medical Monitor discusses and reviews potential participants and helps the investigator ensure that only participants who are appropriate and who meet the protocol inclusion and exclusion criteria are enrolled in the study. The Medical Monitor also ensures that the protocol-specified procedures are followed, especially safety and tolerability data, and that there are no potential safety concerns. The Medical Monitor will review all SAE's regarding this study and any Severe AEs and clinically significant safety concerns.

Regarding the reproductive safety of this study, a reproductive safety monitoring committee will be formed consisting of three fertility experts – these fertility experts should have previously served on a reproductive safety monitoring committee – and the medical monitor. This reproductive safety monitoring committee will convene after the first 4 patients enrolled and then quarterly thereafter to review the reproductive parameters.

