#### Stopping rules:

Stopping rules will be developed with the help and guidance of the fertility experts after the first 4 patients are enrolled and sufficient information is available about the baseline sperm counts seen for this population.

Regarding the nonreproductive safety of this study, this will be monitored by the medical monitor together with the NC-008 safety monitoring committee (comprising the medical monitors and sponsor study physician for the trial). This NC-008 safety monitoring committee is an appointed group of physicians that are currently monitoring study NC-008. In this study (NC-008) patients with pulmonary TB are being treated with the same (BPaMZ) antibiotic treatment regime. The Medical Monitor will participate in teleconferences with this NC-008 safety monitoring committee to review all SAE and Severe AEs regarding this and any safety concerns that are new or are being tracked.

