## 10.2 Sample Size

To assess the male reproductive safety profile of pretomanid in the regimen (BPaMZ) of Bedaquiline 200mg daily for 8 weeks then 100 mg daily for 18 weeks, together with pretomanid 200 mg (1x daily) + moxifloxacin 400 mg (1x daily) + pyrazinamide 1500 mg (1x daily) for 26 weeks in participants with Drug-sensitive (DS) or Drug-resistant (DR) pulmonary TB.

The sample size is not based on formal statistical considerations. It is based on practicality of enrolment and to rule out any severe effect of the regimen on semen parameters.

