1.0 / 15 Feb 2021	Initial version	
1.1 / 20 Dec 2022	Updates made to outcome analysis and circulated for comment	
1.2 / 30 Jan 2023	Updates made to Statistical analysis and circulated for further comments	
1.3/ 06 Feb 2023	Updates made to outcome sections to align more with the protocol Additional analysis details added	
1.4/ 02 Mar 2023	Updates made post expert review	
1.5/ 14 Mar 2023	Further updates made after expert review	
1.6/ 17 April 2023	Updates made to section on pharmacokinetics	

1. Introduction

This document outlines the statistical analysis for the BPaMZ/SEM trial, Protocol Version 4.0, dated 07 April 2022.

Pretomanid is being used in an antimicrobial combination regimen(s) to treat patients with pulmonary tuberculosis. The primary purpose of this trial "BPaMZ/SEM" is to evaluate the potential effect of pretomanid on human testicular function whilst being used in a 26-week antimicrobial combination regimen consisting of bedaquiline (B) plus pretomanid (Pa) plus moxifloxacin (M) and pyrazinamide (Z) (BPaMZ).

All participants will receive the same regimen of BPaMZ once daily for 26 weeks.

The participant population will be patients with drug resistant TB (DR-TB) defined as Mycobacterium tuberculosis (MTB) that is sensitive to fluoroquinolones but

- 1. Mono-resistant to rifampicin or isoniazid, OR
- 2. Resistant to both rifampicin and isoniazid (MDR-TB)

2. Objectives

The primary objective is to assess the male reproductive safety of pretomanid in the regimen (BPaMZ) of bedaquiline 200mg (200mg daily for 8 weeks then 100 mg daily for 18 weeks), together with pretomanid 200 mg (1x daily) + moxifloxacin 400 mg (1x daily) + pyrazinamide 1500 mg (1 x daily) for 26 weeks in participants with Drug-resistant (DR) pulmonary TB.

The secondary objective is to evaluate the efficacy, safety and tolerability after 26 weeks of active treatment for TB and follow up for 52 weeks after start of the above described treatment regimen in participants with Drug-resistant (DR) pulmonary TB.

3. Sample Size

A total of 20 evaluable male participants diagnosed with DR-TB who completed the trial will be required.

Twenty-five participants (25) will be enrolled in the trial assuming a 20% participant dropout of the trial. If the dropout rate is higher than 20% before finishing 26 weeks of treatment, the enrolment of additional participants may be considered to assure that 20 complete.

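### The trial is meant to rule out a severe effect on sperm production, but the SAP plans no confidence interval for any semen outcome, so its tables will not state how large a fall the data still allow

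*SAP*

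**What the plan says.** **The aim.** The protocol synopsis states: "This study is intended to rule out clinically significant severe adverse effects on testicular function". Protocol 10.2 says the sample size has no formal statistical basis and continues: "It is based on practicality of enrolment and to rule out any severe effect of the regimen on semen parameters". SAP 3 repeats this for sperm production. The formal primary objective (Protocol 3.1, SAP 2) is milder: to assess male reproductive safety.

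**The size.** SAP 3: "A total of 20 evaluable male participants diagnosed with DR-TB who completed the trial will be required". Enrolment is 25, allowing for 20% dropout.

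**The analysis.** SAP 9 makes all analysis descriptive. For the primary endpoint, SAP 9.1: "The change from baseline in total sperm count at 26 weeks will be summarised by mean, standard deviation, median, IQR and range". SAP 9.2 plans the same statistics for the other continuous outcomes, and counts, percentages and shift tables for the rest. That includes the SAP 5 proportions of men whose count or concentration rises or falls by at least 50% at Weeks 26 and 44. Protocol 10.4 restates the endpoints and refers the detail to the SAP.

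**What counts as severe.** Neither document gives a size. On stopping, Protocol 9.4 says: "Stopping rules will be developed with the help and guidance of the fertility experts after the first 4 patients are enrolled".

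**The concern.** To rule something out is a statement about the limits of uncertainty. Mean, SD, median, IQR, range and percentages describe the men observed; they do not say what fall in the wider population is still compatible with what was seen. A table entry of 0 (0%) men with a halved count, from a trial described as able to rule out severe harm, invites a stronger reading than some 20 men can carry. The sample size has no formal basis and there is no control arm, so precision has to be shown in the results because it was not built into the design.

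**Working it through.** **1. The plan's own figure.** 20 evaluable / (1 − 0.20) = 25. This reproduces. The 20 itself cannot be reproduced, because no SD, margin, alpha or power is given.

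**2. Search for an interval.** SAP 5, 9.1, 9.2 and 9.3 and Protocol 10.2 to 10.4 contain none for a semen outcome. The error bars in SAP 9.3 and Protocol 10.6 belong to drug-concentration plots. The confidence interval in Protocol 2.2.1.4 is a past result of another trial.

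**3. Proportion with at least a 50% fall (no SD needed).** Exact two-sided 95% upper limit = 0.975 quantile of Beta(x+1, n−x). For x = 0 this is 1 − 0.025^(1/n); at n = 20, 1 − 0.025^(1/20) = 0.168.

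| Men with the fall | n = 20 | n = 25 |
|---|---|---|
| 0 | 16.8% | 13.7% |
| 1 | 24.9% | 20.4% |
| 2 | 31.7% | 26.0% |

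**4. Mean change.** The 95% half-width is t/√n in SDs of the change: 2.093/√20 = 0.468 SD, and 2.064/√25 = 0.413 SD. The documents give no SD, so this cannot be turned into a sperm count in advance.

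**5. Median (change or within-man ratio).** The interval from the r-th smallest to the r-th largest value has coverage 1 − 2·P(Bin(n, ½) ≤ r−1).
- n = 20, 6th to 15th: 1 − 2 × 0.0207 = 95.9%.
- n = 25, 8th to 18th: 1 − 2 × 0.0216 = 95.7%.

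The ratio interval stays defined if some Week 26 counts are zero. The denominator should be positive, because Protocol 6.2 excludes "Evidence at screening of azoospermia" and baseline averages that sample with a second one. This is not guaranteed: SAP 7.4 foresees men entered despite failing entry criteria, and SAP 8.1.1 keeps every dosed man in the ITT population.

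**6. Why the median ratio cannot stand alone.** Its lower limit is above 0.5 as long as no more than r−1 men are at or below half of baseline: 5 of 20 (25%; exact 95% CI 8.7% to 49.1%) or 7 of 25 (28%; 12.1% to 49.4%). All of those men could be azoospermic. The per-man proportion has to be read beside it.

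**7. Illustration on an assumed SD.** Suppose log(Week 26/baseline) is normal with mean 0, so there is no true effect. The chance that one man shows a 50% fall is p = Φ(ln 0.5/SD). The median interval excludes a halving with probability P(Bin(20, p) ≤ 5) or P(Bin(25, p) ≤ 7).

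| Assumed SD | p | n = 20 | n = 25 |
|---|---|---|---|
| 0.6 | 0.124 | 0.970 | 0.991 |
| 0.8 | 0.193 | 0.826 | 0.907 |
| 1.0 | 0.244 | 0.641 | 0.750 |
| 1.2 | 0.282 | 0.488 | 0.592 |
| 1.5 | 0.322 | 0.336 | 0.417 |

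Whether about 20 men can exclude even a halving of the median therefore depends on a variability that the documents do not state.

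**The case against.** **The plan is openly descriptive.** The objective is to assess, the size is declared informal, and the ruling-out language sits in a synopsis line and the sample-size rationale. This stands, and it limits the weight of the point. It does not remove it, because a confidence interval is estimation and needs neither a hypothesis test nor a power calculation.

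**Readers can work out the intervals.** Largely true. A t-interval for the mean change follows from mean, SD and n, and exact intervals for the proportions follow from the counts. A reader might infer that the ratio interval is out of reach without participant-level data. That goes too far. SAP 9.3 item 4 plots percentage change in sperm count at Week 26 against mean trough; if drawn man by man, ordered values could be read off for men with drug levels. SAP 9 mentions listings, and Protocol 14 requires the data behind publications to be open. What stands is that the planned tables do not report the interval.

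**A one-sided bound is as natural for harm.** At zero events it is 1 − 0.05^(1/n): 13.9% for 20 men and 11.3% for 25. That is somewhat tighter, with the same message.

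**The 50% proportion partly measures within-man variation.** Under the illustration, 0 of 20 would occur in about 7% of trials at SD 0.6 (0.876^20) and 0.04% at SD 1.5 (0.678^20) with no drug effect. This stands, and it is why the interval for the proportion should be read beside those for the group change and the ratio.

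**Severe effects are watched for in other ways.** Hormones, shift tables and expert review all contribute: "This reproductive safety monitoring committee will convene after the first 4 patients enrolled and then quarterly thereafter to review the reproductive parameters". None of them supplies an interval. A reader might also infer that no threshold for severe exists anywhere. The documents do not support that, since stopping rules were to be developed later and may contain one.

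**Conclusion.** The point holds as a gap between stated aim and planned output, and it should be fixed. The documents speak of ruling out a severe effect, yet none of the planned semen tables states what the data exclude. Even the most favourable result on the 50% criterion leaves an upper limit of 16.8% at n = 20 or 13.7% at n = 25.

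A reader might conclude that the analysis is invalid or the primary endpoint unusable. The documents do not support that: the summaries are legitimate description, match the formal objective, and contain most of what is needed to derive the intervals.

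The exact limits rest only on the counts and on n. A Week 26 n of 20 to 25 is an expectation under the dropout assumption. It may be lower if completers lack samples, since SAP 7.6 uses complete cases without imputation, or higher if men are replaced or added (Protocol 6, SAP 3). The log-normal table is illustration only.

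**What to change.** In SAP 9.1 and 9.2 keep the planned summaries and add:

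1. A 95% CI for the primary endpoint as defined: the mean change (t-interval), the median change (order-statistic interval), or both, in total sperm count at Week 26.
2. As a supplement on the relative scale already used in SAP 5 and 9.3, the median within-man ratio Week 26/baseline with its exact order-statistic CI at the n available (6th to 15th at n = 20, 8th to 18th at n = 25). State that any man with a zero baseline entered in error is left out of the ratio and listed.
3. Exact 95% CIs for the proportion with at least a 50% fall, reported separately from rises, and for azoospermia at Week 26, read beside items 1 and 2.
4. The same intervals at Week 44.

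Word the conclusion as what these limits exclude. If the sponsor wants to claim that a severe effect is ruled out, it should record before the Week 26 analysis what size counts as severe, and disclose what accumulating semen data were known to those who set it, given the quarterly expert review. Otherwise, reword the synopsis objective, Protocol 10.2 and SAP 3 as descriptive.

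Cost: some SAP wording and a few lines of code; no new patients, samples or visits. The downside is that intervals may look less reassuring than point summaries. Without a control arm they also cannot separate a drug effect from recovery from TB or from within-man variation, and the report should say so.

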9.2. Secondary outcome analyses

The following applies to outcomes outlined in sections 5 and 6. Continuous outcomes will be summarised by mean, standard deviation, median, interquartile range and range. For change from baseline, both baseline value and change from baseline will be summarised.

Binary and categorical outcomes will be summarised with n's and percentages. Shift tables will be provided to summarise the status changes from baseline to week 13, week 26 and week 44. Each shift table will include shift analyses from within the reference range at baseline to above the reference range at 13, 26 or 44 weeks and from within the reference range at baseline to below the reference range at the same time points.

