# 1.1.1 Synopsis Flow Chart and Procedures

	Period	Screening								Tre	atme	nt							F	ollow	Up				
Footnote	Visit	Day -21 to -1	Day 1 (Baseline)	Week 2	Week 3	Week 4	Week 5	Week 6	Week 7	Week 8	Week 12	Week 12 to 13	Week 16	Week 22	Week 26 (EOT)	Week 26 to 27	Week 35	Week 44	Week 44 to 45	Week 52	Week 65	Week 78	Early Withdrawal		
a	Visit Window	N/A			+/- 3 days								+/-7 days					+/-14 days							
	Written Informed Consent	x																							
	Demography/Medic al Treatment/Smoking History	x																							
	Inclusion/Exclusion	Х	Х																						
b	Sputum Sampling	Х	X			Х				X	Х		Х	Х	Х		X	Х		X	х	X	Х		
с	HIV Status and CD4 Count	x																							
d	Urine Drug Screen	Х																							
е	Safety Laboratory Test	x	х	x	х	х	x	x	х	x	Х		х	x	х								х		
f	Semen Sampling	QX	BX									XXf				XXf			XXf				XXf		
g	Male Reproductive Hormone Tests	x		x		х				x	х		х		х		x	x		x	x	x	х		
h	12-Lead ECG	Х	X	Х	Х	Х	х	Х	Х	Х	Х		Х		Х			x					Х		
i	Chest X-Ray	X													Х										
	Vital Signs and Weight	x	х	x	x	х	x	x	х	x	х		х	x	х		x	x		x	x	x	х		
j	Physical Exam – Full	x	х																				X		
j	Physical Exam – Limited			x	х	х	х	x	x	x	х		х	x	х		х	х		x	х	x			
TN	IP-C-SOP01-B V1.0 30-JAN	1-2019		CO	NFIC	TMP-C-SOP01-B V1.0 30-JAN-2019 CONFIDENTIAL																			

CONFIDENTIAL Page 15 of 79

TB Alliance Protocol Number: Pa-824-CL-012 Protocol Version: V4.0 07 APR 2022 Protocol Name: BPaMZ/SEM

	Period	Screening			Treatment									Follow Up									
Footnote	Visit	Day -21 to -1	Day 1 (Baseline)	Week 2	Week 3	Week 4	Week 5	Week 6	Week 7	Week 8	Week 12	Week 12 to 13	Week 16	Week 22	Week 26 (EOT)	Week 26 to 27	Week 35	Week 44	Week 44 to 45	Week 52	Week 65	Week 78	Early Withdrawal
a	Visit Window	N/A		+/- 3 days						+/-7 days						+/-14 days							
k	Pharmacokinetic Sampling			x		x				x	x		x	х	х			x					х
Т	IMP Assignment		Х																				
m	IMP dispensing and compliance Check			х	х	х	х	x	х	х	х		х	х	х								Х
	Concomitant Medications	x	х	x	х	х	x	x	х	х	х		х	х	х		x	x		х	х	x	х
	Adverse Events	X	Х	Х	Х	X	x	X	Х	х	Х		Х	х	Х		X	X		Х	Х	Х	Х
n	Investigator Assessment														х			x				x	х
0	Paternity Questionnaire																					x	х

TMP-C-SOP01-B V1.0 30-JAN-2019

CONFIDENTIAL Page 16 of 79 GENERAL: Vital signs, ECGs and blood draws are to be performed pre-dosing unless otherwise specified. Vital signs and/or ECGs should be done prior to blood draws (safety and PK) on days with those assessments.

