In follow-up to the non-clinical findings, males in the 8-week Phase 2 Trial NC-002-(M-Pa-Z) were evaluated by plasma sampling for the reproductive hormones Luteinizing Hormone (LH), FSH and Testosterone at baseline and at the end of the treatment period. If the trial drug regimen caused testicular toxicity, the most sensitive measure from these hormones would be an increase in levels of FSH. Among participants in the M-Pa100-Z group the mean baseline FSH was 9.027 U/L which decreased to 8.338 U/L at the end of therapy (N=21 with samples at baseline and Day 56). Among participants in the M-Pa200-Z group the mean baseline FSH was 6.531 U/L at baseline, and this decreased to a mean of 6.061 at the end of therapy (N=19 with samples at baseline and Day 56). Men in the rifampicin 150 mg plus isoniazid 75 mg plus pyrazinamide 400 mg plus ethambutol 275 mg combination tablets (HRZE) control group had a mean baseline of 7.394 U/L which decreased to 6.714 at the end of therapy (N=23 with samples at baseline and Day 56). This gives relative reassurance that pretomanid is not likely to cause testicular toxicity in men.

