The sample size is not based on formal statistical considerations. It is based on practicality of enrolment and to rule out any severe effect of the regimen on sperm production.

4. Primary Outcome

The primary outcome (endpoint) will be change from baseline in total sperm count at 26 weeks of therapy.

5. Secondary male reproductive toxicity outcomes

1. Change from baseline in all semen parameters (semen count and semen concentration) at 13,

26 and 44 weeks.

- 2. The proportion of subjects experiencing an increase or decrease in sperm count and sperm concentration from baseline to the timepoint of interest (26 weeks and 44 weeks) will be calculated.
- 3. The proportion of subjects experiencing at least a 50 percent increase or decrease in sperm count and sperm concentration from baseline to the timepoint of interest (26 weeks and 44 weeks) will be calculated.
- 4. Change from baseline (at screening) in male reproductive hormones at Week 2, 4, 8, 12, 16, 26, 35, 44, 52, 65, 78 and at early withdrawal. Reproductive hormones: luteinizing hormone (LH), follicle-stimulating hormone (FSH), Inhibin B, testosterone, and total testosterone
- 5. Plasma concentration of pretomanid from sparse sampling will be summarised as descriptive statistics.

6. Other secondary outcomes

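### SAP 9.2 sets shift tables only at the semen weeks (13, 26, 44), so 8 to 9 of 11 hormone draws enter no count of men leaving the reference range

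*SAP*

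**What the plan says.** SAP 9.2 opens with its scope: "The following applies to outcomes outlined in sections 5 and 6". Section 5 holds the semen and hormone outcomes; section 6 holds TB efficacy and safety, including laboratory measurements. SAP 9.2 then states: "Shift tables will be provided to summarise the status changes from baseline to week 13, week 26 and week 44". It adds: "Each shift table will include shift analyses from within the reference range at baseline to above the reference range at 13, 26 or 44 weeks", with the mirror-image shift to below the range at the same weeks. It does not name the parameters that get a shift table.

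The schedules come from three places:

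- **Semen (SAP 5, item 1):** "Change from baseline in all semen parameters (semen count and semen concentration) at 13", and then at 26 and 44 weeks.
- **Hormones (SAP 5, item 4):** change from the screening value "in male reproductive hormones at Week 2, 4, 8, 12, 16, 26, 35, 44, 52, 65, 78 and at early withdrawal".
- **Safety laboratory (Protocol 1.1.1 flow chart, row "Safety Laboratory Test"):** after baseline, Weeks 2 to 8, 12, 16, 22, 26 and early withdrawal.

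**The concern.** The three shift-table weeks fit the semen schedule and are carried over to measurements taken at other times. The trial has a single arm, aims for 20 evaluable men and is analysed descriptively (SAP 3 and 9), so the tables are the whole analysis. A shift table shows how many men began inside the reference range and left it; a group summary does not.

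This matters most for FSH. The Background in Protocol 2.1, discussing an earlier study that measured LH, FSH and testosterone, says that under testicular toxicity "the most sensitive measure from these hormones would be an increase in levels of FSH". Take a man whose FSH is in range at screening, above range at Week 8, 16, 35 or 52, and back in range at Weeks 12, 26 and 44. He would appear in no shift table. Nor would a man whose first excursion came at Week 52 or later.

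**Working it through.** The plan gives no figure to reproduce, so the check is a count of scheduled weeks after baseline against the set {13, 26, 44}.

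**Step 1: match by week label.**

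| Measurement | Scheduled weeks after baseline | Number | In {13, 26, 44} | Outside |
|---|---|---|---|---|
| Hormones | 2, 4, 8, 12, 16, 26, 35, 44, 52, 65, 78 | 11 | 26, 44 | 11 − 2 = 9 |
| Safety laboratory | 2, 3, 4, 5, 6, 7, 8, 12, 16, 22, 26 | 11 | 26 | 11 − 1 = 10 |

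**Step 2: allow for visit windows.** SAP 7.5 gives the Week 12 visit a window of ±7 days, which reaches Week 13, and times events by visit date rather than week number. Protocol 1.1.1 (footnote f) collects the first on-treatment semen pair at Weeks 12-13 and labels its average the Week 12 value. Week 12 blood results might therefore fill the Week 13 column, though the SAP does not say so. No other window (±3, ±7 or ±14 days) brings a further visit onto Week 13, 26 or 44. With Week 12 counted:

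- hormones: 11 − 3 = 8 outside;
- safety laboratory: 11 − 2 = 9 outside.

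**Step 3: split the hormone draws by period.**

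- On treatment (Weeks 2, 4, 8, 12, 16, 26): 6 draws, of which 1 or 2 are in a shift table, so 5 or 4 are outside.
- After treatment (Weeks 35, 44, 52, 65, 78): 5 draws, of which 1 is in a shift table, so 4 are outside. Weeks 52, 65 and 78 are all among these.
- Total outside: 5 + 4 = 9, or 4 + 4 = 8, which agrees with Steps 1 and 2.

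**Step 4: count early withdrawal as a twelfth draw.** By week label, 10 of 12 hormone draws and 11 of 12 safety-laboratory draws are outside.

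**Step 5: look for another table that counts men out of range.**

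- *Hormones.* SAP 9.2 gives mean, SD, median, IQR and range for baseline and change, at all weeks listed in SAP 5 item 4. The range shows the most extreme change at each visit. It does not show how many men crossed a limit or whether they started inside it. SAP 5 items 2 and 3 count individual men, but only for sperm count and concentration. SAP Table 1 covers AST, ALT, bilirubin, ALP and lipase, and the DMID table in Protocol Appendix 2 grades no reproductive hormone.
- *Safety laboratory.* SAP 6.2 item 5 plans newly notable grade 3 or 4 values. SAP 7.6 includes abnormalities after baseline that are new or of higher grade, and SAP 7.7 counts a newly notable value with no limit on the visit.

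**The case against.** The strongest reply is that the tables were meant for semen only. SAP 9.2 names no parameter, and the three weeks are exactly the semen weeks, so on that reading nothing is mis-scheduled. This is a fair account of where the weeks came from, but it conflicts with the section's own scope sentence. It would also leave hormones with no shift table at all: 0 of 11 draws instead of 2 or 3.

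Three stronger readings are tempting, and the documents do not support them:

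- **That the omitted hormone draws go unanalysed.** They are summarised at every scheduled week, and a marked rise in one man would show in the range. The reproductive safety monitoring committee also reviews the reproductive parameters quarterly (Protocol 9.4), and a change that the investigator judges clinically significant becomes an adverse event (Protocol 9.2.2). What is missing is the count of men leaving the range.
- **That the Week 13 column asks for blood data that cannot exist.** The Week 12 window reaches Week 13, so the mapping is unstated rather than impossible. Week 44 is different for safety laboratory tests: none is scheduled then.
- **That laboratory toxicity between the three weeks would be missed.** SAP 6.2, 7.6 and 7.7 cover abnormalities at any visit, although Table 1 is limited to liver tests and lipase.

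It is also fair to say that the FSH remark ranks FSH only among the hormones measured in that earlier study, and that this trial measures sperm count directly as its primary endpoint. Hormones are supporting evidence. Even so, Protocol 4.2 makes them a key secondary endpoint.

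**Conclusion.** The point holds for hormones. Under SAP 9.2 as written, 8 to 9 of 11 scheduled draws after baseline enter no shift table, and no other planned table counts men who move out of the reference range. The lower figure assumes that Week 12 blood results fill the Week 13 column; the higher one assumes that they do not. Both assume that the scope sentence means what it says and hormones do get shift tables. With 20 evaluable men, each man not counted is 1/20 = 5% of the group.

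For safety laboratory tests the mismatch is 9 to 10 of 11 draws, with none at Week 44. It is mainly a matter of tidiness, because abnormalities are captured elsewhere.

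The primary endpoint is not affected. This is a low-cost improvement to the reporting of a key secondary endpoint.

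**What to change.** Amend SAP 9.2 as follows:

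1. Name the parameters that get shift tables.
2. Keep Weeks 13, 26 and 44 for semen, and state that the Week 13 value is the pair collected at Weeks 12-13.
3. For LH, FSH, inhibin B and testosterone, tabulate shifts against the reference range at each scheduled draw.
4. For the same hormones, add the worst on-treatment value (Weeks 2-26) and the worst post-treatment value (Weeks 35-78). Fix the direction in advance: highest for FSH and LH, lowest for inhibin B and testosterone.
5. For any safety-laboratory shift table, use weeks at which those tests are drawn.

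No new visits, samples or tests are needed. Four hormones at 11 draws give 4 × 11 = 44 visit-level shifts, and two worst values each add 4 × 2 = 8. This fits in a few tables. The downside is that a worst value over 5 or 6 draws picks up more chance excursions than a single visit, and there is no control arm to show how many to expect. The worst-value tables should therefore sit beside the per-visit shifts, so that a reader can see whether an excursion was isolated or sustained.
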